Satisfaction and Acceptability Questionnaire	Y/C			X	X
Device Downloads	Y		X	X	X
Fingerstick Blood Sample	D		X	X	X
Medical Record/Patient Record	D		X	X	X

8.2 Sample Size Considerations and Power Analysis:

Sample size for this study is based on our preliminary work with this intervention in epilepsy (i.e., Epilepsy Journey), which found moderate to large effect sizes from baseline to 6-month follow-up, ranging from $d = 0.55$ to $d = 0.93$ for the Global Executive Composite Score, the composite measure of the Behavior Rating Inventory of Executive Function, which represented our barriers outcome of interest. Additionally, preliminary data on our primary outcomes collected at CCHMC from 2016-2017 (i.e., Stress/Burnout and Time Pressure/Planning subscales) show that our patients improve slightly over one year with Enhanced Standard of Care, corresponding to an effect size of $d = 0.19$. A Monte Carlo simulation in Mplus with $n = 5000$ replications was conducted assuming: 1) proper handling of missing data; 2) 25% attrition; 3) standardization of all analysis variables; 4) at least 30% of the error variance in our primary outcome ($R^2 = 0.30$) being explained by baseline barriers scores and covariates; 5) we will observe the smallest effect size from our preliminary work in the treatment group (i.e., $d = 0.55$); and 6) we will observe a small improvement in our control group ($d = 0.19$). **Recent interim analyses and meetings with our NIH program officer have yielded a change in our study design from a fully powered RCT to detect subgroup differences to a pilot RCT focused on feasibility, acceptability, satisfaction and preliminary efficacy differences between the control and treatment groups. These new analyses indicate the need for a total sample size of $n=190$ ($n=95$ in the control group and $n=95$ in the treatment group).**

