In March 2022, due to the COVID-19 pandemic and slow recruitment, we made a number of changes, approved by NIDDK, to our protocol. For Aim 3, these included lowering our age eligibility to 12 years old, making the age range 12-17 years. We also eliminated our exclusion criteria regarding use of metformin and asthma medications as these had no impact on the science of our study. We also reduced the sample size from N=256 to N=190 based on our preliminary data and considered the study a pilot trial. We eliminated the final follow-up assessment from required to optional, and reverted to 1:1 randomization for the treatment and control group allocation. Finally, to minimize missing data, we modified procedures to ensure our primary outcome was captured at our primary endpoint (Follow-up 1) at a minimum to ensure we could make valid causal inferences. Thus, we made the Barriers to Diabetes Adherence questionnaire the only required measure for completion prior to randomization or moving to subsequent timepoints. Because HbA1c could be collected from chart reviews, we were confident about obtaining these data, as well as basic measures of adherence from the medical chart.

Study Hypotheses

Primary Aim: Examine feasibility, acceptability, and preliminary efficacy of *Diabetes Journey* to reduce adherence barriers (PRO) in adolescents with T1D over time.

Hypothesis: The treatment group will find the treatment acceptable and feasible and demonstrate significant improvements in barriers, adherence, HbA1c, and HRQOL.

Study Design

This study was a multi-site RCT designed to evaluate the efficacy of the *Diabetes Journey* mHealth intervention aimed at reducing barriers to T1D self-management among adolescents. These barriers include stress/burnout, executive dysfunction, and time management challenges. Participants were randomized into two groups: *Diabetes Journey* intervention or Enhanced Standard of Care, using stratified block randomization. The study was conducted across multiple sites and followed participants at baseline, post-treatment, and follow-ups at 6 and 12 months.

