Adolescents endorsing clinically elevated adherence barriers during routine clinical care (primary outcome and intervention target-Barriers to Adherence scale) were randomized to: 1) *Diabetes Journey* or 2) Enhanced Standard of Care. For *Diabetes Journey*, each mHealth module accompanied a telemedicine session to review skills and problem-solve adolescent-identified goals with a therapist. For Enhanced Standard of Care, adolescents received handouts and phone calls from a certified diabetes educator.

Power and Sample Size Estimates

Initially, sample size estimates were based on the Epilepsy Journey study, which found moderate to large effect sizes from baseline to 6-month follow-up, ranging from $d = 0.55$ to $d = 0.93$ for the Global Executive Composite Score of the Behavior Rating Inventory of Executive Function. We also used Barriers to Diabetes Adherence questionnaire data collected as part of routine care from adolescents who attended T1D medical appointments at Cincinnati Children's Hospital Medical Center (CCHMC) from 2016-2017, which showed improvement across one year on Stress/Burnout and Time Pressure/Planning subscales ($d = 0.19$). A Monte Carlo simulation in Mplus with $n = 5,000$ replications was conducted assuming: 1) proper handling of missing data; 2) 25% attrition; 3) standardization of all analysis variables; 4) $>30\%$ of the error variance in our primary outcome ($R^2 = 0.30$) explained by baseline Barriers to Diabetes Adherence questionnaire scores and covariates; 5) smallest effect size from our preliminary work in the treatment group (i.e., $d = 0.55$); and 6) small improvement in Enhanced Standard of Care ($d = 0.19$). Our analysis indicated $>80\%$ power to detect a follow-up group difference effect size of $\Delta d = 0.36$ (where $\Delta d = 0.55 - 0.19$) with a total sample size of $N = 256$, with $n = 100$ in Enhanced Standard of Care and $n = 156$ in *Diabetes Journey*.

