Given recruitment challenges and the resulting changes to eligibility and randomization, we decided to focus on the overall *Diabetes Journey* versus Enhanced Standard of Care difference at our primary endpoint, instead of powering for treatment subgroup comparisons. Using the same effect size estimates and assumptions in the original power analyses, but assuming a 1:1 randomization to only two groups, we determined that reducing the sample size from $N = 256$ to $N = 190$ ensured $>80\%$ power to detect a follow-up group difference effect size of $\Delta d = 0.36$, resulting in final group sizes of $n = 110$ in *Diabetes Journey* and $n = 80$ in Enhanced Standard of Care.

Randomization

At baseline, all participants who met inclusion/exclusion criteria (e.g., elevations on the Stress/Burnout and/or Time Pressure/Planning subscales of the Barriers to Diabetes Adherence questionnaire) were randomized to either the control group (i.e., Enhanced Standard of Care) or treatment group (i.e., *Diabetes Journey*). We used stratified block randomization with two strata and blocks of size 2 or 4 chosen randomly within each stratum. Stratification was based on baseline HbA1c (i.e., $>9\%$ or $<9\%$), site (i.e., CCHMC or University of Florida/University of

Colorado's Barbara Davis Center for Diabetes), and Barriers to Diabetes Adherence elevation type within the treatment arm (i.e., elevated on one or both of the subscales). The HbA1c criterion was selected because the average HbA1c in 13-17 year olds with T1D in the US is 9%, which resulted in comparable sample sizes above and below 9%. In addition, although the American Diabetes Association recommends an HbA1c <7%, very few adolescents achieve this. Site was chosen to ensure balance for any site-related differences. The randomization list was held by an individual independent of the study to reduce any potential biases. Those who were randomized were notified of their randomization status after completion of the baseline questionnaires so intervention materials could be provided immediately.

Measures

Definitions and Derivations (numbers at the end of variable names represent timepoint: 0=baseline; 1=post-treatment, 2=follow-up1 and 3=follow-up2)

Barriers to Diabetes Adherence (BDA) (Mulvey et al., 2011)				
Subscale	Descriptor	Items	Range	Interpretation
bdastress	BDA Stress and Burnout Subscale	4	1-5	↑ scores ↑ stress and burnout

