An intent to treat approach will be undertaken for all analyses. We will examine the data for intervention group comparability using chi-square tests for categorical variables (e.g., biological sex, insurance status, technology use) and t-tests for continuous variables (e.g., age, T1D duration) prior to analysis of the primary outcomes. Should we observe intervention group

differences at baseline on any variables, these variables will be added to the outcome models as covariates.

Our primary hypothesis examines group differences at the 6-month follow-up (i.e., primary end point) given that we expect participants to have made the most significant gains from the intervention after implementing the acquired skills for some time. Two separate Analysis of Covariance models (one for each barrier subscale) will be used to test the primary hypothesis that the *Diabetes Journey* intervention group will demonstrate significantly lower barriers compared to the Enhanced Standard of Care group at 6-month follow-up, after controlling for baseline barriers. For secondary outcomes (i.e., HRQOL, T1D self-management behaviors, HbA1c), the same analytical approach will be used, with baseline values of the respective outcome included as a covariate. To evaluate the treatment effect on our primary and secondary outcomes across time, we will employ Generalized Estimating Equations (GEE), while controlling for baseline covariates.

Handling Missing Data

Missing data will be addressed using full information maximum likelihood (FIML) under the assumption of data missing at random (MAR) in the ANCOVA models. For the longitudinal GEE models, we will use multiple imputation to address missing data under the assumption that the data are Missing at Random (MAR). The imputation will use chained equations (mi impute chained) with relevant predictors to generate 100 imputed datasets.

Variables:

Outcome variables:

- Primary: BDA subscale scores for stress and time pressure (bdastress, bdatime)
- Secondary: alc, T1DAL subscales and total score (t1dalhandlingt1d, t1daltpeer, t1daltfamily, t1dalemotionr, t1daltotalr)
- **Group (independent variable):**
 - condition (0 = ESC, 1 = DJ)
- **Timepoints:**
 - time (post-treatment = 1, follow-up 1 = 2, follow-up 2 = 3)
- **Covariates:**
 - age (continuous)
 - sex (categorical, 0 = male, 1 = female)
 - insurance (insur, 0=public, 1=private)
 - time since dx (timedx, continuous)
 - use of technology (cgm yes = 1, cgm no = 0)

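### The SAP's claim of more than 80% power at N=190 cannot be reproduced from its stated inputs at two-sided 5% (about 72%), and the settings that could reach it are not given

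*SAP*

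**What the plan says.** The SAP's Power and Sample Size Estimates section first describes the N=256 plan (156 Diabetes Journey, 100 Enhanced Standard of Care). It claims more than 80% power for a standardized difference of 0.55 − 0.19 = 0.36. The listed assumptions include "2) 25% attrition; 3) standardization of all analysis variables", with R² = 0.30 from baseline barriers and covariates. No visit is attached to the 25%.

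For the reduced trial the SAP works "Using the same effect size estimates and assumptions in the original power analyses, but assuming a 1:1 randomization to only two groups". It says that N=190 secures more than 80% power for the same 0.36, and reports group sizes of 110 and 80.

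Protocol 8.2 repeats the assumptions, words R² as a floor ("at least 30% of the error variance in our primary outcome"), and introduces the new total with "These new analyses indicate the need for a total sample size of" 190, split 95/95. It states no power percentage.

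The primary hypothesis is directional: the "intervention group will demonstrate significantly lower barriers compared to the Enhanced Standard of Care group at 6-month follow-up". It is tested by two ANCOVAs, one per subscale. Neither document gives alpha, sidedness, or a rule for whether one subscale or both must succeed.

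**The concern.** A total of 256 was said to give just over 80% power. Cutting it to 190 with effect size, attrition and R² unchanged should lower the power noticeably, and equal allocation buys back little. Yet the same claim is made for both totals.

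This is the only power figure for the final sample size. Enrolment is complete and the trial is called a pilot, so what is at stake is how the 6-month result is read. Someone who trusts the figure will take the chance of missing a true 0.36 difference to be under 20%. On the stated values at two-sided 5% it is about 28% for each subscale, so a non-significant result would be weaker evidence against that difference than the SAP implies.

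**Working it through.** **Inputs**

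| Input | Value | Source |
|---|---|---|
| Difference | 0.36 SD | SAP, power section |
| R² | 0.30 | SAP, power section; Protocol 8.2 |
| Attrition | 25% | same |
| Allocation, N=256 | 156/100 | SAP, power section |
| Allocation, N=190 | 95/95 planned; 110/80 reported | Protocol 8.2; SAP, power section |
| Alpha and sidedness | 5%, two-sided | **assumed**; not stated |
| Success rule | one subscale | **assumed**; not stated |

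**Formula.** With m = n × (1 − attrition) per arm, SE = √[(1 − R²)(1/m₁ + 1/m₀)]. Power comes from the noncentral t with noncentrality 0.36/SE and m₁ + m₀ − 3 degrees of freedom.

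**Step 1: the N=256 claim.** m = 117 and 75. SE = √[0.70 × (1/117 + 1/75)] = 0.1238, noncentrality 2.909, 189 df. Power is **82.5%**, which agrees with the SAP if 156/100 is read as a two-arm contrast.

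**Step 2: the N=190 claim, same inputs.**
- 95/95: m = 71.25 per arm, SE = 0.1402, noncentrality 2.568. Power is **72.3%**.
- 110/80: m = 82.5 and 60, SE = 0.1420, noncentrality 2.536. Power is **71.2%**.

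An ANCOVA simulation with random dropout (60,000 replicates) gives 82.0%, 71.9% and 70.6% for the three designs.

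The information term n₁n₀/(n₁ + n₀) falls from 156 × 100/256 = 60.9 to 95 × 95/190 = 47.5, a loss of 22%. Equal allocation recovers little: 128/128 would give only 84.3%.

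**Step 3: the difference detectable at 80% power**, same inputs: 0.395 at 95/95 and 0.400 at 110/80.

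**Step 4: what would bring N=190 to 80% or more** (95/95 unless noted)

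| Change from the Step 2 inputs | Power |
|---|---|
| One-sided 5% | 81.9% (110/80: 81.0%) |
| No attrition | 83.9% |
| 6-month loss 9.7% (110/80: 7.4%) | 80% |
| R² 0.42 | 80% |
| Loss 12.5% and R² 0.33 | 80.5% |
| Loss 15% and R² 0.35 | 80.5% |
| 110/80, loss 12.5% and R² 0.35 | 80.7% |
| At least one of two subscales, test statistics correlated 0.5 or 0.7 (assumed) | about 86% or 83% |

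A partial reduction in loss is not enough alone: 12.5% with R² still 0.30 gives 78.7% (110/80: 77.7%).

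**Step 5: missing-data method.** The SAP says "Missing data will be addressed using full information maximum likelihood (FIML) under the assumption of data missing at random (MAR) in the ANCOVA models". With only baseline covariates in the model, a participant without a 6-month score adds no information on the adjusted group difference. A post-treatment score used as an auxiliary variable could recover some, but none is named for the ANCOVA.

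**The case against.** The strongest reply is that Step 2 does not show the sponsor's figure to be wrong. It came from a simulation whose settings are not reported in full, and several readings exceed 80%.

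- **Sidedness.** One-sided 5% fits both claims (89.5% at N=256, 81.9% at 95/95). But the directional wording states a hypothesis; no one-sided test is declared.
- **Inputs.** R² = 0.30 is worded as a floor. The 25% may belong to a later visit, since the SAP says the study "followed participants at baseline, post-treatment, and follow-ups at 6 and 12 months". The SAP also says "we modified procedures to ensure our primary outcome was captured at our primary endpoint (Follow-up 1) at a minimum", so 6-month loss may be lower. The SAP ties the reduction in N to preliminary data, and Protocol 8.2 mentions interim and new analyses, so unseen inputs are possible. That would sit uneasily with the statement that the assumptions were the same.
- **Success rule.** With two primary subscales and no rule, the figure could be power for at least one. The documents do not say so.
- **The N=256 match.** Protocol 8.2 says the earlier design was powered for subgroup differences. If, for illustration, the 156 were two equal subgroups each compared with 100 controls, the formula gives 69%. Agreement at 82.5% is therefore supportive, not proof of the method.

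All of this stands as a limit on the conclusion. None of it supplies the missing settings.

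A reader might also infer that 110/80 contradicts 1:1 allocation. The documents do not support that: the SAP's Introduction dates the return to 1:1 to March 2022, so earlier unequal allocation could have produced the imbalance. It needs an explanation, not a correction.

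**Conclusion.** The concern holds in conditional form. For one subscale, at two-sided 5%, with 25% of 6-month scores missing and R² = 0.30, power at N=190 is about 72% (95/95) or 71% (110/80), and about 0.40 is detectable at 80% power. More than 80% is reached only under settings the documents do not state. The shortfall at 95/95 therefore runs from zero to about 8 points (80 − 72.3 = 7.7), depending on what was used.

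A reader might go further and conclude that the sponsor's simulation was in error, or that the trial should have been larger. For scale, 80% at 1:1 on the stated values would take N=230. The documents support neither conclusion: alpha, sidedness and success rule are unstated, so the figure is unreproduced rather than disproved, and the trial is a completed pilot. What is established is that the carried-over assumptions, as written, do not deliver the claim at the conventional level.

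**What to change.** In the SAP power section, state the alpha, sidedness, success rule (each subscale or at least one), 6-month attrition and R² used for N=190. Then:

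- If they were two-sided 5% per subscale on the stated values, replace the claim of more than 80% with about 72% at 95/95 and 71% at 110/80, and give about 0.40 as the difference detectable at 80% power.
- If they were anything else, remove the statement that the assumptions were unchanged, and report the inputs and the power that follows.

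Add one sentence on how 110/80 arose given the 95/95 in Protocol 8.2 (for example, unequal allocation before March 2022, if that is the reason). Interpret a non-significant 6-month result through its confidence interval.

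The cost is a few sentences. No patients are added, and neither the estimand nor the test changes. The downside is that the stated power may become less favourable.

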6. SELECTION & RECRUITMENT OF PARTICIPANTS

Study Participants

Study participants will include n=190 adolescents, ages 12-17, with T1D and their caregivers from Cincinnati Children's Hospital Medical Center (CCHMC), the University of Florida (UF) and the University of Colorado Barbara Davis Center for Diabetes (BDC). Adolescents and caregivers will be recruited during routine diabetes clinic visits and will meet the following inclusion/exclusion criteria:

Inclusion Criteria

- T1D diagnosis >1 year
- Adolescents with T1D ages 12-17
- Elevations on the Barriers to Diabetes Adherence questionnaire (scores of ≥ 2 of 5 for the Stress/Burnout and/or Time Pressure/Planning subscales) based on their previous clinic visit scores
- Ability to read/speak English (all measures are in English)

Exclusion Criteria

- Diagnosis of significant developmental disorders (e.g., autism spectrum disorder, moderate/severe developmental or intellectual disability)
- Comorbid medical diagnoses (e.g., cystic fibrosis) with the exception of endocrine disorders (e.g., Celiac disease, thyroid)

Recruitment Procedures

Potential participants meeting eligibility criteria will be identified by a trained research assistant in collaboration with the members of the Diabetes teams at each site. Specifically, patients will be pre-screened based on their scheduled appointments for inclusion/exclusion criteria.

Elevations on the BDA is one of our inclusion criteria for study entry. At CCHMC and the University of Florida, BDA elevations will most often be identified by reviewing responses from the patient's clinic visit or through a screening process. For eligible participants who do not have a completed Barriers to Diabetes Adherence (BDA) measure, study coordinators may administer a screening BDA to determine further study eligibility, but only after informed consent/assent is obtained. If the participant does not have any elevations on the BDA, they will be deemed a screen-fail and will not participate in the Diabetes Journey intervention. If the participant completes the BDA at a later clinic visit and has elevations on the BDA that make them eligible for study participation, and study staff determine they still meet all other inclusion criteria, the participant may be re-consented for study participation at that time.

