stratum will be used and stratification will be based on baseline A1C (i.e., $\geq 9\%$ or $< 9\%$), site (i.e., CCHMC, the University of Colorado Barbara Davis Center or the University of Florida), and Barriers to Diabetes Adherence elevation type within the treatment arm (i.e., elevated on one or both of the subscales). The A1C criterion was selected because the average A1C in 13-17 year olds with T1D in the US is 9%, which will result in comparable sample sizes above and below 9%. In addition, although the American Diabetes Association recommends an A1C $< 7\%$, very few adolescents achieve this. Site was chosen as a stratification variable to ensure balance for any site-related differences. This randomization strategy will minimize imbalance of the number of participants across groups. The randomization list will be held by an individual independent of the study to reduce any potential biases. Participants will be notified of their randomization group within 3 business days of completion of baseline data and be provided with appropriate materials (e.g., log-in information or website information and links). Total treatment time is up to 12 weeks, which coincides with routine quarterly T1D clinic appointments. This also enables sufficient time for cancelled and/or rescheduled sessions that are likely to occur given adolescents' busy schedules.

Control Group (Enhanced Standard of Care)

Participants randomized to Enhanced Standard of Care will receive general education via the T1DToolkit website, as well as 4 Zoom sessions (e.g., Zoom for Healthcare; See Appendix C) with certified diabetes educators (CDEs) from either CCHMC or UF across 12-weeks. Notably, if technical difficulties arise, telephone sessions will be conducted and audio recorded. Content to address adherence barriers were modified and or newly developed for the Enhanced Standard of Care group via the T1DToolkit website. Depending on the participant's elevated score(s) on the Barriers to Diabetes Adherence scale, patients will receive information specifically addressing elevated scales of the BDA. Treatment fidelity will be assessed via audio recordings and completion of checklists, which will be reviewed weekly by [name] with the CDEs who deliver this intervention.

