number, and password protected to ensure privacy. A medical chart review will also be conducted to gather information about hemoglobin A1C, data downloaded from devices, medications, comorbidities, hospitalizations, and time since diagnosis.

It is the goal for all participant families to complete their baseline visit prior to being randomized to intervention. This will include completion of questionnaires and download data from their T1D device. However, participating families may be randomized if the primary outcome measure (BDA) and a baseline A1C within 4 weeks of enrollment is available, at a minimum. Participants will have an opportunity to complete baseline questionnaires until the initiation of the first intervention session. Device downloads will not be required for randomization as these data can be retrieved from the medical record.

After completion of the required questionnaires and A1C at a minimum will be randomized to either: Diabetes Journey or Enhanced Standard of Care (Figure 1). Stratified block randomization with two strata and blocks of size 2 or 4 chosen randomly within each

Modules	T1Dtoolkit.com links
Stress and Burnout	
Burnout	https://t1dtoolkit.org/for-teens-young-adults/burnout-2/
Sharing responsibility	https://t1dtoolkit.org/for-teens-young-adults/sharing-responsibility/
Strategies to Manage Pain	https://t1dtoolkit.org/uncategorized/strategies-to-manage-pain/
Building a Support Network	https://t1dtoolkit.org/uncategorized/building-a-support-network/
Time Pressure and Planning	
Setting Reminders	https://t1dtoolkit.org/for-teens-young-adults/setting-reminders/
Prioritizing and Planning	https://t1dtoolkit.org/for-teens-young-adults/14472/
Organization of Your Environment	https://t1dtoolkit.org/for-teens-young-adults/organizing-your-environment/
Eating on Your Own	https://t1dtoolkit.org/for-teens-young-adults/eating-on-your-own/

Treatment (Diabetes Journey)

[figure not shown]

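### BDA elevation type is listed as a stratification factor inside the treatment arm only, so as written its one/both split is balanced between arms only by chance

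*SAP*

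**What the plan says.** Three bases for stratification are listed in the Protocol (section 8, Study Procedures) and the SAP (Randomization): baseline HbA1c around 9%, site, and "Barriers to Diabetes Adherence elevation type within the treatment arm (i.e., elevated on one or both of the subscales"). The third item is worded identically in both documents.

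On the number of strata, the SAP says "We used stratified block randomization with two strata and blocks of size 2 or 4 chosen randomly within each stratum", and the Protocol says "Stratified block randomization with two strata and blocks of size 2 or 4 chosen randomly within each" stratum. The site factor differs. The Protocol has three levels, "site (i.e., CCHMC, the University of Colorado Barbara Davis Center or the University of Florida"), while the SAP pools two centres, "site (i.e., CCHMC or University of Florida/University of" Colorado's Barbara Davis Center).

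Elevation type is available for everyone before allocation. Under section 8 of the Protocol, families "may be randomized if the primary outcome measure (BDA) and a baseline A1C within 4 weeks of enrollment is available", so the BDA is a minimum requirement in both arms. The same section uses elevation type to choose content in the control arm as well as modules in the treatment arm.

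On the purpose of the comparison, the SAP (Power and Sample Size Estimates) says "we decided to focus on the overall *Diabetes Journey* versus Enhanced Standard of Care difference at our primary endpoint, instead of powering for treatment subgroup" contrasts.

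In the SAP's Statistical Analyses section, the primary ANCOVAs control for baseline barriers, and the covariate list includes baseline outcome scores, site and several characteristics. Elevation type is not on that list. Variables that differ between groups at baseline are to be added to the models.

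**The concern.** A stratification factor works because its value is fixed before the arm is drawn and because separate allocation sequences run within each of its levels. A factor defined only among participants already assigned to treatment does neither. It leaves the one/both mix in the control arm free, and so leaves the difference between arms free.

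The factor is worth balancing. It is derived from the two primary outcome scales at entry, and it determines whether a Diabetes Journey participant is scheduled for 5 or 8 sessions. Nothing in the documents explains restricting it to one arm, given that it is known for all participants and the SAP has settled on the overall two-arm contrast. The restriction may be left over from the design with treatment subgroups, but the documents do not say so.

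There is also a reporting problem. From these texts a reader cannot tell which sequences were used, because the stated number of strata does not fit the listed factors.

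**Working it through.** **1. The stated number of strata.** The only figure in the text is two strata. Multiplying the levels of the listed factors:

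| Site coding | HbA1c × site | with elevation type in both arms |
|---|---|---|
| SAP (2 levels) | 2 × 2 = 4 | 4 × 2 = 8 |
| Protocol (3 levels) | 2 × 3 = 6 | 6 × 2 = 12 |

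No crossing gives two, so the figure is not reproduced. It fits only if it means two stratifying variables (HbA1c and site), and that reading leaves elevation type out of the allocation altogether.

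**2. Chance imbalance when elevation type does not constrain the arms.** Let p be the proportion elevated on both subscales. It is not given, so 0.3, 0.5 and 0.7 are assumed. Group sizes are 95:95 (Protocol, section 8.2) and 110:80 (SAP, Power and Sample Size Estimates). The 95% limit for the difference in proportions is 1.96 × √[p(1−p)(1/n1 + 1/n2)].

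- p = 0.5, 95:95: 1.96 × √(0.25 × 2/95) = 1.96 × 0.0725 = 0.142
- p = 0.5, 110:80: 1.96 × √(0.25 × 0.02159) = 1.96 × 0.0735 = 0.144
- p = 0.3 or 0.7, 95:95: 1.96 × √(0.21 × 2/95) = 1.96 × 0.0665 = 0.130
- p = 0.3 or 0.7, 110:80: 1.96 × √(0.21 × 0.02159) = 1.96 × 0.0673 = 0.132

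**3. Simulation of the two schemes.** Permuted blocks of 2 or 4, 1:1, N = 190, 2,000 replicates, two or three sites, p = 0.3, 0.5, 0.7, with HbA1c and site levels assumed equally common:

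| | Elevation type not stratified | Stratified in both arms |
|---|---|---|
| SD of the difference (points) | 6.6–7.5 | 1.2–1.7 |
| 95th percentile of the absolute difference (points) | 12.6–14.7 | 2.2–3.2 |
| Chance of 10 points or more | 12–18% | about 0% |

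**4. Possible effect on the contrast.** Suppose elevation on both subscales shifts the outcome by 0.2 to 0.4 SD beyond what the model already adjusts for. The documents do not support any particular value; this range is an assumption.

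- At the 95% limit: 0.14 × 0.2 = 0.028 SD to 0.14 × 0.4 = 0.056 SD, which is 8–16% of the target 0.36.
- At one SD of imbalance (about 7 points): 0.014 to 0.028 SD, which is 4–8% of 0.36.
- Standard error of the contrast with the plan's R² = 0.30 and 25% attrition (95 × 0.75 = 71.25 per arm): √[0.70 × (2/71.25)] = 0.14 SD. The limit case is therefore 0.2 to 0.4 standard errors.
- Precision gained by adjusting: at p = 0.5 the factor explains 0.25 × 0.2² = 0.01 to 0.25 × 0.4² = 0.04 of a residual variance of 0.70. The standard error falls by 1 − √(0.69/0.70) = 0.7% to 1 − √(0.66/0.70) = 2.9%.

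**The case against.** A reader might infer that the arms are unbalanced on the entry criterion, that the comparison is biased, or that the randomisation was faulty. The documents support none of these.

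- Every participant meets the entry criterion. Only its one/both subtype is at issue.
- Randomisation balances the subtype in expectation. Chance imbalance on an unstratified factor is already covered by the standard error, and type I error stays valid.
- The list itself is not in the documents. It may have used elevation type in both arms, in which case only the wording is wrong.
- The Protocol's statement that the strategy minimises imbalance concerns the number of participants per group, so this point does not contradict it.
- The 5 or 8 sessions concern the dose within one arm and do not by themselves confound the arms.

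Two further objections have weight. First, the SAP's reference to baseline barriers in the primary ANCOVAs does not clearly exclude the other subscale. If both continuous baselines are in the model, a one/both indicator adds little. Second, the SAP would add any variable found to differ at baseline. That rule is a partial safeguard only: it depends on the observed data, does not name elevation type, and gives no threshold. If it is judged by a chi-square test at 0.05, it acts only at a gap of about 13 to 14 points.

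These objections reduce the likely harm to something small. They do not resolve what the text says about the allocation, or the mismatch between two strata and three factors.

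**Conclusion.** The point holds as a reading of both documents: elevation type, as described, cannot balance the arms, and no other text applies it to control participants at randomisation. What is lost is enforced balance (95% limits of about ±13 to 14 points instead of about 2–3) and a clear account of how participants were allocated. It is not a bias.

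The balance figures assume 30–70% elevated on both subscales, and the 2–3 point figure assumes 1:1 blocks throughout. The shift of 0.03 to 0.06 SD pairs an assumed effect with an extreme imbalance, so the usual shift would be smaller. Whether the allocation itself or only its description is at fault cannot be settled from the documents. The change is worth making because it is nearly free, not because the trial's conclusion is at risk.

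**What to change.** 1. **Establish and report what was done.** From the actual randomisation list, state whether elevation type was a pre-randomisation factor in both arms, how site was coded, and how many strata existed. Then correct section 8 of the Protocol and the SAP's Randomization section to match. Remove the restriction to the treatment arm only if the list shows stratification in both arms. Otherwise state that the factor was not balanced across arms. The SAP describes the randomisation as completed, so deleting the phrase without checking could make a true record false.

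2. **Prespecify the covariate in either case.** Derive the one/both indicator for both arms from the BDA used to qualify the participant and assign content before randomisation. Say which administration that is, because the Protocol's schedule allows both a screening and a baseline BDA and the two may disagree. Include the indicator in both primary ANCOVAs and in the GEE models, so that adjustment does not depend on an observed baseline difference.

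The cost is wording in two places and one degree of freedom per model, using data already held.
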